	
 • Change from baseline on the SF-36 physical component summary (PCS) and mental component summary (MCS) • Change from baseline on PatGA of disease severity • Change from baseline for the WPAI-PSO scores (Absenteeism, Presenteeism, Work Productivity Loss, and Activity Impairment) • Change from baseline in QIDS-SR16 total score in those with a baseline QIDS-SR16 total score ≥ 11 • Proportion of patients achieving a DLQI total score of (0,1) with at least a 5-point improvement (reduction) from baseline in patients with a baseline DLQI total score ≥ 5 • Proportion of patients achieving DLQI (0,1) with DLQI baseline score > 1

To assess whether 250 mg mirikizumab Q8W and 125 mg mirikizumab Q8W dosing is superior to placebo with respect to maintenance of high and highest levels of clinical response among patients who have an PASI 90 at Week 16 and are re-randomized
 
To assess the efficacy of 250 mg mirikizumab Q8W following relapse after re-randomization to placebo treatment in the Maintenance Dosing Period
 
To evaluate the pharmacokinetics and pharmacokinetic/pharmacodynamic relationship of mirikizumab
	
At Week 52 and at various time points during the Maintenance Dosing Period:
 
 • Time to relapse (the loss, at any visit, of $\geq 50\%$ of the Week 16 PASI improvement from baseline). • Proportion of patients who have relapsed. • Proportion of patients maintaining clinical response (PASI 90) after re-randomization at the start of the randomized withdrawal period • Incidence of disease rebound within 12 weeks (worsening of psoriasis severity over baseline sPGA score, or worsening of psoriasis severity over baseline PASI score by 125%, or change in psoriasis phenotype [for example, from plaque to pustular]) after re-randomization to placebo at Week 16. 
During the Maintenance Dosing Period:
 
 • Proportion of patients who regained PASI 90 within 16 weeks after mirikizumab retreatment. • Clearance and volume of distribution of mirikizumab • Relationship between mirikizumab exposure and efficacy (sPGA and PASI)

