10.3.1.1. Missing Data Imputation

The following methods for imputation of missing data will be used:

- *Non-Responder Imputation (NRI) for Binary Clinical Response:* Patients will be considered non-responders for the NRI analysis if they do not meet the clinical response criteria or have missing clinical response data at the analysis time point. Randomized subjects without at least 1 postbaseline observation will also be defined as non-responders for the NRI analysis.
- *Mixed-Effects Model for Repeated Measures (MMRM):* It will be the primary analysis method for longitudinal continuous measurements. It assumes missing at random and the bias caused by missing data can be attenuated by modelling random effects using the within-patient error correlation structure.

Additional missing data imputation methodologies, for example, modified baseline observation carried forward (mBOCF), may be considered as sensitivity analyses and will be detailed in the SAP. By using mBOCF, for patients discontinuing study treatment due to an AE, the baseline observation will be carried forward to the corresponding primary endpoint for evaluation. For patients discontinuing investigational product for any other reason, the last nonmissing postbaseline observation before discontinuation will be carried forward to the corresponding primary endpoint for evaluation.

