6.3. Handling of Dropouts or Missing Data

Intercurrent events (ICH E9R1) are events which occur after the treatment initiation and make it impossible to measure a variable or influence how it should be interpreted. Examples of such events include treatment discontinuation due to death or adverse events (AEs), rescue treatment, and loss to follow-up. The missing data methods described below handle intercurrent events in different ways.

6.3.1. *Non-Responder Imputation (NRI)*

The NRI method can be justified based on the composite strategy (ICH E9R1) for handling intercurrent events. In this strategy patients are defined as responders only if they meet the clinical requirements for response at the predefined time AND they remain on the assigned study treatment. Failing either criteria by definition makes them non-responders.

Analysis of binary efficacy and health outcome variables will be assessed using an NRI method. Patients will be considered as non-responder for the NRI analysis if they do not meet the clinical response criteria or have missing clinical response data at the analysis time point. Randomized patients with no postbaseline observations will also be defined as non-responders for the NRI analysis.

For the Maintenance Period, patient who relapse (see definition in [Table AMAK.6.5](#)) after re-randomization during the maintenance period will be considered to have entered the relapse period and will be non-responders for all subsequent visits of maintenance efficacy analysis.

For the Relapse Period, the response rates will be summarized by the weeks after relapse based on the number of patients with planned scheduled visit during the Relapse Period. Patients who complete the Week 52 treatment visit will, thereafter, not be counted in the numerator when calculating the response rate.

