6.3.4. As Observed

Summary based on observed data at each postbaseline visit will be provided for some endpoints. Descriptive statistics will be reported without inferential comparisons. Only data from completers at the visit are relevant, and therefore the analysis does not need to deal with missing data. This estimand is based on the subset of patients who would complete treatment through visit if assigned to it. Therefore, this estimand is conditional and targets the effect of treatment conditional on completion of treatment through the time point of interest. Because the estimand is defined for a subpopulation conditional on an intercurrent (post-randomization) event, it is not causal. The strategy used in this estimand is the one behind the so-called “observed cases” or “completers” analysis ubiquitous in the literature but is not one of the recommended strategies in the ICH E9(R1).

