	
(5) self-criticism;
	
Interest
	
Item #13 (general interest).
	
Domain is missing if the item is missing.

	
(6) suicidal ideation;
	
Energy/fatigue
	
Item #14 (energy level).
	
Domain is missing if the item is missing.

	
(7) interest;
	
Psychomotor agitation/retardation
	
The highest score recorded for the two psychomotor items: #15 (feeling slowed down) and #16 (feeling restless).
	
Domain is missing if all items are missing.

	
(8) energy/fatigue;
	
QIDS-SR16 Response
	
≥50% improvement in the QIDS-SR16 total score from baseline.
	
If total score is missing for baseline or visit, then missing.

	
(9) psychomotor agitation/retardation
	
QIDS-SR16 Remission
	
QIDS-SR16 Total Score of 0 to 5.
	
If total score is missing, then missing.

Measure	Description	Variable	Derivation/Comment	Definition of Missing Components
Facial Psoriasis	Physician assessed presence or absence of facial psoriasis.	Facial Psoriasis	Response is either Yes or No.	Missing if question is missing.

Abbreviations: BSA = body surface area; DLQI = Global Assessment Dermatology Life Quality Index; EMA = European Medicines Agency; HRQoL = health-related quality of life; MCID = Minimal Clinically Important Difference; MCS = Mental Component Score; NRS = Numeric Rating Scales; PASI = Psoriasis Area and Severity Index; PatGA = Patients Global Assessment of Psoriasis; PCS = Physical Component Score; Ps = psoriasis; PSS = Psoriasis Symptoms Scale; PSSI = Psoriasis Scalp Severity Index; SAP = statistical analysis plan; SDTM = study data tabulation model; sPGA = Static Physician Global Assessment; UK = United Kingdom; VAS = visual analog scale.

Table AMAK.6.6. Description of Efficacy/Health Outcomes Analyses

Measure	Variable	Analysis Method (Section 6.1.4)	Population (Section 6.1.1)	Time Point
PASI	PASI 90 (Primary and Sensitivity)	CMH analysis with NRI	Induction ITT; Induction PPS	Week 16 (and all visits in corresponding Periods)
		Logistic regression analysis with NRI	Induction ITT	Week 16 (and all visits in corresponding Periods)
		Categorical MMRM	Induction ITT	Week 16 (and all visits in corresponding Periods)
	PASI 75; PASI 90; PASI 100	CMH analysis with NRI	Induction ITT; Re-randomized Maintenance ITT;	All visits in corresponding periods
		Summary statistics with NRI and as observed	Non-re-randomized Maintenance; Re-randomized Relapsed	All visits in corresponding periods

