	Time to relapse	KM analysis (censoring described in Table AMAK.6.5)	Re-randomized Maintenance ITT	All visits in corresponding periods
	Regaining PASI 90 within 16 weeks after relapse and retreatment	Summary statistics (As observed)	Re-randomized Relapsed	16 weeks after relapse
	Time to first regaining PASI 90 after relapse	KM analysis (censoring described in Table AMAK.6.5)	Re-randomized Relapsed	All visits in corresponding periods
sPGA	sPGA (0,1) (Primary and Sensitivity)	CMH analysis with NRI	Induction ITT; Induction PPS	Week 16 (and all visits in corresponding Period)
		Logistic regression analysis with NRI	Induction ITT	Week 16 (and all visits in corresponding Period)
		Categorical MMRM	Induction ITT	Week 16 (and all visits in corresponding Period)
	sPGA (0,1); sPGA (0)	CMH analysis with NRI	Induction ITT; Re-randomized Maintenance ITT;	All visits in corresponding periods
		CMH analysis with NRI	Re-randomized Maintenance ITT - In Patients who Achieve sPGA (0,1) at Week 16	All visits in corresponding periods
		Summary statistics with NRI and as observed	Non-re-randomized Maintenance; Re-randomized Relapsed	All visits in corresponding periods
	Time to first loss of sPGA (0,1)	KM product limit curve (censoring described in Table AMAK.6.5)	Re-randomized Maintenance ITT - In Patients who Achieve sPGA (0,1) at Week 16	All visits in corresponding periods
	Time to first achieving sPGA (0,1)	KM product limit curve (censoring described in Table AMAK.6.5)	Induction ITT	All visits in corresponding periods
BSA	Proportion of patients with $\leq 1\%$ of BSA with psoriasis involvement	CMH analysis with NRI	Induction ITT; Re-randomized Maintenance ITT	All visits in corresponding periods
		Summary statistics with NRI and as observed	Non-re-randomized Maintenance	All visits in corresponding periods
	BSA change from baseline	MMRM; ANCOVA with mBOCF	Induction ITT; Re-randomized Maintenance ITT	All visits in corresponding periods

Measure	Variable	Analysis Method (Section 6.1.4)	Population (Section 6.1.1)	Time Point
PSS	PSS Symptoms Score of 0	CMH analysis with NRI	Induction ITT - In Patients with Baseline PSS Symptom Score ≥ 1	All weeks in Induction Period
		CMH analysis with NRI	Re-randomized Maintenance ITT - In Patients with Baseline PSS Symptom Score ≥ 1	All visits in corresponding period
		Summary statistics with NRI and as observed	Non-re-randomized Maintenance - In Patients with Baseline PSS Symptom Score ≥ 1	All visits in Maintenance Periods

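### PASI 90 regained within 16 weeks of retreatment is summarised as observed only and has no written derivation, so the recapture rate is likely, though not certainly, too high

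*SAP*

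**What the plan says.** Protocol Section 4 (Table AMAK.2) sets this other-secondary objective: "To assess the efficacy of 250 mg mirikizumab Q8W following relapse after re-randomization to placebo treatment in the Maintenance Dosing Period". Its one efficacy endpoint is "Proportion of patients who regained PASI 90 within 16 weeks after mirikizumab retreatment".

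In SAP Table AMAK.6.6 the matching row is "Regaining PASI 90 within 16 weeks after relapse and retreatment", in the Re-randomized Relapsed population at 16 weeks after relapse. The method cell reads "Summary statistics (As observed", and no other method is listed. SAP 6.3.4 explains the term: "Only data from completers at the visit are relevant, and therefore the analysis does not need to deal with missing data". It adds that this estimand conditions on a post-randomization event, is not causal, and is not a strategy that ICH E9(R1) recommends.

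Other parts of the plan take a different line:

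- SAP 6.3.1 states: "Analysis of binary efficacy and health outcome variables will be assessed using an NRI method". It bases Relapse Period rates on patients with a planned visit at that number of weeks after relapse.
- Protocol 10.3.1.1 classes as non-responders those who "have missing clinical response data at the analysis time point".
- The by-visit PASI 75/90/100 row of Table AMAK.6.6 covers the same relapsed population and specifies "Summary statistics with NRI and as observed".

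Table AMAK.6.5 defines relapse and time to regaining PASI 90. It does not define regaining within 16 weeks.

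**The concern.** Failure of retreatment is itself a route out of the analysis. Under Protocol 5.1.3 and 5.1.4, a patient who stops goes to the early termination visit and then to follow-up, where other psoriasis therapy is allowed. Under Protocol 8.2, a patient who needs another effective agent must leave before starting it. Such a patient has no 16-week value on retreatment and, on a completers-only reading, is not counted.

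This rate would support a statement that patients who relapse after withdrawal can be successfully retreated. If it describes only those who stayed on retreatment, it answers a narrower question than the protocol endpoint asks. The general NRI rule and the table row also conflict, so a programmer has to choose between them.

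Late relapse raises a second question. Dosing ends at Week 48 and the last assessment of the period is at Week 52, so some retreated patients cannot have 16 weeks of follow-up. The row does not say how they are counted.

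**Working it through.** **The plan's own figure.** The documents state no recapture rate, number of relapsers or Relapse Period dropout. The nearest stated figure is the size of the re-randomized arms (Protocol 10.1, SAP 5.1): 400 × 0.70 / 3 = 93.3, which matches the stated 93 per arm. Power for 80% vs 10% and for 70% vs 10% at two-sided 0.025 is above 0.999, consistent with the stated >95%. These figures do not fix the size of the issue, because relapse (loss of at least half the Week 16 improvement) is a stricter event than loss of PASI 90.

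**Who can reach 16 weeks.** Protocol 5.1.3 starts retreatment at the visit where relapse is found. The possible visits are Weeks 20, 24, 28, 32, 36, 40, 44 and 48.

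- Starts at Weeks 20 to 36 (5 of 8 visits) can reach 16 weeks, since 36 + 16 = 52.
- Starts at Weeks 40, 44 and 48 (3 of 8) leave 52 − 40 = 12, 52 − 44 = 8 and 52 − 48 = 4 weeks.

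**As observed against NRI.** Let d be the share stopping before 16 weeks, r the regain probability among stayers, and q the share of stoppers who had regained before stopping. All three are assumptions.

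- As observed, completers at 16 weeks only: r
- NRI with regained at any visit up to 16 weeks: r(1 − d) + dq
- Gap: d(r − q)

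With q = 0 the gap is d × r, in percentage points:

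| r | d = 2% | d = 5% | d = 10% | d = 20% |
|---|---|---|---|---|
| 60% | 1.2 | 3.0 | 6.0 | 12.0 |
| 80% | 1.6 | 4.0 | 8.0 | 16.0 |
| 90% | 1.8 | 4.5 | 9.0 | 18.0 |

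For example, with r = 80% and d = 10%, NRI gives 0.80 × 0.90 = 72%, a gap of 8 points. If stoppers regain half as often as stayers (q = 40%), the gap is 0.10 × (0.80 − 0.40) = 4 points. If they regain equally often it is 0. If q = 90% it is 0.10 × (0.80 − 0.90) = −1 point, so the direction reverses.

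**NRI applied to every relapser.** This errs the other way. With no dropout and r = 80%, counting relapsers found after Week 36 as failures gives 0.80 × 0.90 = 72%, 0.80 × 0.80 = 64% or 0.80 × 0.70 = 56% if they are 10%, 20% or 30% of relapsers. The loss is administrative and says nothing about the drug.

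**Day count.** Week 36 is Day 253 ± 5 and Week 52 is Day 365 ± 5 (Protocol Section 2). The nominal interval is 365 − 253 = 112 days, but visits within window can lie up to 370 − 248 = 122 days apart.

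**The Kaplan-Meier analysis.** Table AMAK.6.5 starts the clock for time to regaining at the start of the Relapse Period, and censors non-regainers after their last Maintenance Period visit. Table AMAK.6.3 ends the Maintenance Period, for relapsers, before the Relapse Period begins. Non-regainers would be censored at or before time zero.

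**The case against.** A reader might infer that the rate is certainly biased in favour of mirikizumab. The documents do not support that, because the row has no written numerator or denominator. If within 16 weeks means any observed visit, a patient who stops but has a post-relapse assessment stays in the denominator. PASI is scheduled at the early termination visit, so most stoppers would have one. If it means the value at 16 weeks, patients who regain early and then stop are also lost, which lowers the rate. NRI is itself a composite strategy, so part of any gap is a difference of estimand and not bias.

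A reader might also infer that recapture has no analysis protected against dropout. That is not so. By-visit PASI 90 with NRI is planned in the same population, with a planned-visit denominator, and a time-to-regain analysis is listed. The first is a close substitute, but it measures response at a visit and not regained within 16 weeks. The second censors stoppers, and its censoring date is unworkable as written.

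The stakes are limited. Table AMAK.6.2 plans no comparison in this population, the endpoint is outside the multiplicity-controlled family, and SAP 6.3.4 openly allows as-observed summaries for some endpoints and states their limits.

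What remains is an unexplained departure from the NRI default, on the only efficacy endpoint for the retreatment objective, with no derivation to settle who is counted.

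**Conclusion.** The point stands as a minor-to-moderate defect. As written, the row and SAP 6.3.4 together leave out retreated patients who lack a 16-week value, contrary to the plan's own rule for binary variables. The recapture rate is likely too high, because failed retreatment is a natural reason to stop, but this depends on stoppers regaining less often than stayers.

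The size cannot be derived from the documents. If 80% of stayers regain, 5% to 10% stop and no stopper has regained, the difference from NRI is 4 to 8 points. It halves to 2 to 4 points if stoppers regain half as often, and vanishes if they regain equally often. No confirmatory conclusion is affected.

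**What to change.** 1. In SAP Table AMAK.6.5, define the endpoint as PASI 90 at any scheduled visit up to and including the nominal 16-week post-retreatment visit. Use nominal visits, not a strict 112-day count.
2. In Table AMAK.6.6, change the method to NRI. The denominator is Re-randomized Relapsed patients whose nominal 16-week visit falls by Week 52, that is, first retreatment dose at or before the Week 36 visit. Patients who stop without regaining count as not regained. Keep as observed as supportive.
3. Cover later relapsers with the time-to-regain analysis, after changing its censoring date in Table AMAK.6.5 to the last Relapse Period visit.
4. In SAP 6.3.1, state that patients past Week 52 leave the denominator as well as the numerator. The present text names only the numerator.

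The cost is one new derivation, one method cell and two corrected sentences, with no new data collection. The reported rate is likely to be slightly lower and to rest on fewer patients.

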9.1.2.7.3. Work Productivity and Activity Impairment Questionnaire: Psoriasis

The Work Productivity and Activity Impairment-Psoriasis (WPAI-PSO) Questionnaire is a patient-reported instrument developed to measure the impact on work productivity and regular activities attributable to a specific health problem (psoriasis). It contains 6 items that measure: 1) employment status, 2) hours missed from work due to the psoriasis, 3) hours missed from work for other reasons, 4) hours actually worked, 5) degree of health affected-productivity while working, and 6) degree of health affected-productivity in regular unpaid activities. Four scores are calculated from the responses to these 6 items: absenteeism, presenteeism, work productivity loss, and activity impairment. Scores are calculated as impairment percentages (Reilly et al. 1993), with higher numbers indicating greater impairment and less productivity, that is, worse outcomes.

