Treatment comparisons of continuous efficacy and health outcome variables with a single postbaseline time point will be made using analysis of covariance (ANCOVA) with the following in the model: treatment group, baseline value, and Induction Period/Maintenance Period covariates mentioned in Section 6.2. Type III tests for LSMeans will be used for statistical comparison between treatment groups. The LSMean difference, standard error, p-value, and 95% CI, unless otherwise specified, will also be reported. Analysis of covariance may also be used in addition to the MMRM approach, by repeating analysis for each time point.

The Kaplan-Meier (KM) product limit method will be used to estimate the survival for several time to event analyses. The hazard ratio and log-rank test stratified by covariates mentioned in Section 6.2 will be reported. Time for all analysis will be described in units of weeks.

For variables that are not collected at each postbaseline visit, data may exist at visits where the variable was not scheduled to be collected. In these situations, data from the early discontinuation visit that do not correspond to the planned collection schedule will be excluded from the MMRM analysis (Andersen and Millen 2013). For by-visit summaries/displays, such as boxplots, the weeks when data was not scheduled to be collected may not be displayed. However, unscheduled assessments within any defined study period will still be used in the shift analyses, and for imputing values for the change from baseline to modified baseline observation carried forward (mBOCF) endpoint analyses.

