		DLQI daily activities domain	Sum of responses of questions #3 and #4: #3. How much has your skin interfered with you going shopping or looking after your home or garden? #4. How much has your skin influenced the clothes you wear?	If 1 question in a domain is missing, that domain is missing.
		DLQI leisure domain	Sum of responses of questions #5 and #6: #5. How much has your skin affected any social or leisure activities? #6. How much has your skin make it difficult for you to do any sport?	If 1 question in a domain is missing, that domain is missing.
		DLQI work and school domain	Sum of responses of questions question #7A and #7B: #7A. Has your skin prevented you from working or studying? #7B. If No: how much has your skin been a problem at work or studying?	If the answer to question #7A is missing, this domain is missing. If #7A is No, and #7B is missing, this domain is missing.
		DLQI personal relationships domain	Sum of responses of questions #8 and #9: #8. How much has your skin created problems with your partner or any of your close friends or relatives? #9. How much has your skin caused any sexual difficulties?	If 1 question in a domain is missing, that domain is missing.

Measure	Description	Variable	Derivation/Comment	Definition of Missing Components
		DLQI treatment domain	Response of question #10: #10. How much of a problem has the treatment for your skin been, for example, by making your home messy, or by taking up time?	If 1 question in a domain is missing, that domain is missing.
WPAI-PSO	The Work Productivity and Activity Impairment-Psoriasis (WPAI-PSO) Questionnaire is a patient-reported instrument developed to measure the impact on work productivity and regular activities attributable to a specific health problem (psoriasis). It contains 6 items that measure: 1) employment for pay status; 2) hours missed from work due to the psoriasis; 3) hours missed from work for other reasons; 4) hours actually worked; 5) degree of health affected-productivity while working; and 6) degree of health-affected productivity in regular unpaid activities. Greater scores indicate greater impairment (Reilly Associates Health Outcomes Research [WWW]).	Employment Status	Yes/No	Missing if question is missing.
		Absenteeism Score (%)	$\frac{Q2}{(Q2 + Q4)} \times 100$	Missing if Q2 or Q4 are missing. Also missing if Employment Status is No.
		Presenteeism Score (%)	$\frac{Q5}{10} \times 100$	Missing if Q5 is missing. Also missing if Employment Status is No.

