		Work Productivity Loss Score (%)	$\left[\frac{Q2}{Q2 + Q4} + \left(1 - \frac{Q2}{Q2 + Q4} \right) \frac{Q5}{10} \right] \times 100$	Missing if Q2, Q4, or Q5 is missing. Also missing if Employment Status is No.
		Activity Impairment Score (%)	$\frac{Q6}{10} \times 100$	Missing if Q6 is missing. May still be present and non-missing if patient is unemployed.
Rebound	Derived from multiple other measurements mentioned in this table.	Rebound	Defined as having one or more of the following: worsening of psoriasis severity over baseline static Physician’s Global Assessment (sPGA) score, worsening of psoriasis severity over baseline PASI score by 125%, or change in psoriasis phenotype (i.e., from plaque psoriasis to any of guttate, pustular or erythrodermic psoriasis) after randomization to placebo at Week 16.	Missing if baseline or observed value of sPGA or PASI is missing.
		Rebound within 12 Weeks, post re-randomized to placebo	Defined has having rebound for any non-missing visit between Week 16 to (and including) Week 28 (12 weeks post re-randomized to placebo).	Missing if rebound is missing for all Visits, Week 16 to Week 28.

Measure	Description	Variable	Derivation/Comment	Definition of Missing Components

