DLQI	DLQI (0,1) and ≥ 5 point reduction from baseline	CMH analysis with NRI	Induction ITT - In Patients with Baseline DLQI ≥ 5 Re-randomized Maintenance ITT - In Patients with Study Baseline DLQI ≥ 5	All visits in corresponding periods
		Summary statistics (as observed)	Non-re-randomized Maintenance - In Patients with Study Baseline DLQI ≥ 5	All visits in corresponding periods
	DLQI (0,1)	CMH analysis with NRI	Induction ITT - In Patients with Study Baseline DLQI > 1 ; Re-randomized Maintenance ITT - In Patients with Study Baseline DLQI > 1	All visits in corresponding periods
	DLQI total score ≥ 5 point reduction from baseline	CMH analysis with NRI	Induction ITT - In Patients with Study Baseline DLQI ≥ 5 ; Re-randomized Maintenance ITT - In Patients with Study Baseline DLQI ≥ 5	All visits in corresponding periods
	DLQI total score and domain scores change from baseline	MMRM; ANCOVA with mBOCF	Induction ITT; Re-randomized Maintenance ITT	All visits in corresponding periods

Measure	Variable	Analysis Method (Section 6.1.4)	Population (Section 6.1.1)	Time Point
	DLQI (0,1) by stability of PASI 90 / PASI 100 at Week 52	CMH analysis with NRI	Re-randomized Maintenance ITT	Week 52
SF-36	SF-36 change from baseline for Domain Scores and PCS and MCS Component Scores	ANCOVA with mBOCF	Induction ITT; Re-randomized Maintenance ITT	Last visit in corresponding periods
	SF-36 Domain score Responder Definition; SF-36 PCS Responder Definition; SF-36 MCS Responder Definition (Defined in Table AMAK.6.5)	CMH analysis with NRI	Induction ITT; Re-randomized Maintenance IT	Last visit in corresponding periods
PatGA	PatGA(0)	CMH analysis with NRI	Induction ITT - in patients with baseline PatGA >0; Re-randomized Maintenance ITT – in patients with baseline PatGA >0	All visits with scheduled measurements in corresponding periods
	PatGA (0,1) and ≥ 2 improvement from baseline	CMH analysis with NRI	Induction ITT – in Patients with baseline PatGA ≥ 2 ; Re-randomized Maintenance ITT – in patients with baseline PatGA ≥ 2	All visits with scheduled measurements in corresponding periods
WPAI-PSO	Change from baseline in WPAI-PSO Scores (Absenteeism, Presenteeism, Work Productivity, Activity Impairment)	ANCOVA with mBOCF	Induction ITT - In Patients with Baseline Employment Status of Yes	Week 16 Visit.
		MMRM; ANCOVA with mBOCF	Re-randomized Maintenance ITT - In Patients with Baseline Employment Status of Yes	All visits with scheduled measurements in corresponding period.

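### WPAI-PSO Activity Impairment is analysed only in patients employed at baseline, although the score is valid without paid work and the protocol endpoint carries no employment limit

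*SAP*

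**What the plan says.** In SAP Section 6.10, one row of Table AMAK.6.6 covers "Change from baseline in WPAI-PSO Scores (Absenteeism, Presenteeism, Work Productivity, Activity Impairment"). Its induction population is "Induction ITT - In Patients with Baseline Employment Status of Yes", analysed at Week 16 by ANCOVA with mBOCF. Its maintenance population is "Re-randomized Maintenance ITT - In Patients with Baseline Employment Status of Yes", analysed by MMRM and by ANCOVA with mBOCF. No other row analyses Activity Impairment.

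Table AMAK.6.5 in the same section gives the scoring rules. For Presenteeism the rule is "Missing if Q5 is missing. Also missing if Employment Status is No". Absenteeism and Work Productivity Loss carry the same employment condition. For Activity Impairment the rule is "Missing if Q6 is missing. May still be present and non-missing if patient is unemployed".

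Protocol Section 9.1.2.7.3 describes the item behind Activity Impairment as the "degree of health affected-productivity in regular unpaid activities". Protocol Section 4, Table AMAK.2, lists the endpoint among the other secondary endpoints for the first 16 weeks as "Change from baseline for the WPAI-PSO scores (Absenteeism, Presenteeism, Work Productivity Loss, and Activity Impairment"), with no employment condition. SAP Table AMAK.4.1 repeats it.

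**The concern.** The SAP recognises Activity Impairment as scorable in patients without paid work, then excludes those patients from its only change-from-baseline analysis. For the three work scores the restriction follows from the instrument. For Activity Impairment nothing in the instrument calls for it, and the SAP gives no reason.

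In induction the analysis therefore covers a narrower population than the protocol endpoint describes. The same endpoint list does name a subset where one is meant, for example scalp involvement for PSSI or a baseline QIDS-SR16 threshold. Eligibility has no employment criterion and no upper age limit, so patients without paid work belong to the trial population, and Activity Impairment is the only WPAI-PSO score they can contribute. The stakes are scope and precision for one sub-score.

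**Working it through.** The plan states no sample size, power or employment rate for WPAI-PSO, so there is no figure to reproduce. The check has two parts.

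**1. What the filter removes.** Apply the Table AMAK.6.5 missing-data rules by baseline employment status, with all other items answered. The ANCOVA in SAP Section 6.1.4 contains "treatment group, baseline value, and Induction Period/Maintenance Period covariates mentioned in Section 6.2", and the MMRM also has a baseline term. A patient therefore needs a baseline score to enter either model.

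| Baseline employment | Three work scores without filter | Removed by filter | Activity Impairment without filter | Removed by filter |
|---|---|---|---|---|
| Yes | usable while employed | nothing | usable | nothing |
| No | no baseline score, not usable even if employed later | nothing | usable | all of it |
| Answer missing | may be usable | yes | usable | yes |

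For baseline employment No, the filter is redundant for the work scores and removes every Activity Impairment value. The last line is the one exception to that redundancy: a blank employment answer with completed work items. It should be rare.

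**2. Size of the loss.** Let f be the share employed at baseline, assumed equal in all arms, with the outcome in SD units and equal variance. Group sizes come from the sample size sections (Protocol 10.1, SAP 5.1): 400 and 100 in induction, about 93 per re-randomized group (3 × 93 = 279).

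- Patients excluded: 500(1 − f) in induction; 279(1 − f) in maintenance.
- Induction SE = √(1/(400f) + 1/(100f)); maintenance pairwise SE = √(2/(93f)).
- SE relative to the full population = 1/√f; 95% CI half-width = 1.96 × SE.

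| f | Excluded, induction | SE, induction | Half-width, induction | Excluded, maintenance | SE, maintenance | Half-width, maintenance | SE ratio |
|---|---|---|---|---|---|---|---|
| 1.0 | 0 | 0.1118 | 0.219 | 0 | 0.147 | 0.287 | 1.00 |
| 0.9 | 50 | 0.1179 | 0.231 | 28 | 0.155 | 0.303 | 1.05 |
| 0.8 | 100 | 0.1250 | 0.245 | 56 | 0.164 | 0.321 | 1.12 |
| 0.5 | 250 | 0.1581 | 0.310 | 140 | 0.207 | 0.406 | 1.41 |

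On placebo in induction the excluded number is 100(1 − f), so 10 to 50 patients for f from 0.9 to 0.5.

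The counts are upper bounds. Questionnaires are given only where a linguistically validated translation exists (Protocol 9.1.2.7). Under mBOCF, patients with no postbaseline observation drop out unless they stopped for an adverse event (SAP 6.3.3).

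**The case against.** The strongest reply is that the two tables do not strictly conflict. Table AMAK.6.5 is a visit-level scoring rule, while Table AMAK.6.6 sets the population by baseline employment. The note on unemployed patients still has a use under the filter: someone employed at baseline who later loses work keeps a valid Activity Impairment score. That stands, so this is a tension rather than a contradiction. In maintenance it is the whole argument, because the protocol lists the endpoint only for the first 16 weeks.

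The choice is also prespecified and rests on a baseline variable. The documents allow departures from the full ITT population in induction where noted. A common denominator for the four scores of one instrument is a reasonable aim, although the SAP does not state it. The protocol names no employed subset for the work scores either, so its silence cannot prove an intention to include unemployed patients. All of this is fair, but none of it supplies a reason to discard valid data, and a supportive analysis can provide the common denominator.

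On size, the maintenance figures ignore relapse. The MMRM uses only visits before the Relapse Period, the sample size assumes only 10% of placebo patients maintain PASI 90, and WPAI-PSO is collected in maintenance at Weeks 28, 40 and 52. Placebo numbers at late visits could be far below 93 whatever the employment share. The absolute maintenance counts and half-widths are therefore unreliable for the MMRM. The ratio 1/√f still applies if employment is unrelated to who remains.

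**Conclusion.** The concern holds. Apart from the rare blank employment answer, the employment filter does nothing for the three work scores and removes collected, scorable Activity Impairment data. In induction it makes the analysed population narrower than the protocol endpoint states.

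The precision loss depends entirely on the employed share, which the documents do not give. The range of 5% to 41% in the standard error is an illustration under an assumed 50% to 90% employed, equal across arms and with equal variance. The comparison remains randomized, so no between-arm bias arises. The endpoint is other secondary and outside the graphical testing scheme. This is a worthwhile correction of limited reach.

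**What to change.** Split the WPAI-PSO row in Table AMAK.6.6:

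- Analyse Activity Impairment in the full Induction ITT and Re-randomized Maintenance ITT populations, with the methods and visits already listed.
- Keep the employed-at-baseline subset for Absenteeism, Presenteeism and Work Productivity Loss.
- If a common population across the four scores is wanted, retain an employed-only Activity Impairment analysis as supportive.
- Report the denominator for each score.

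The cost is one table row. The item is already collected, so no new data or procedures are needed. The only drawback is that the four scores will have different denominators.
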